4.4 Study duration and duration of participant's participation

Students will be regularly approached for data collection. As mentioned above, the data collection phase will start with observation for 50 students selected for the study, and is then followed by collecting hand rinse samples for 12 of them. On the second day of data collection, 25 out of the 50 students will be interviewed with RANAS and well-being survey. The observations will extend for 3 hours and the hand-rinse samples will take about 10 minutes including oral assent. The questionnaire will take a maximum of 20-25 minutes including oral assent as well. The contextual factor survey is expected to take 8-10 minutes from one of the parents to answer.

Entering the students' absenteeism and the pre-defined health outcomes in the diary over the course of the year will not take much time of the teachers. To write down an event of absenteeism will take the teacher about one minute per student.

Finally, some of the students and teachers of the 13 intervention schools will be asked to take part in FGDs or interviews. This should not take them longer than one hour. KIIs with stakeholders outside of the schools will also be limited to one hour.

	2023												2024												
	Jan	Feb	Mar	Apr	May	Jun	Jul	Aug	Sep	Oct	Nov	Dec	Jan	Feb	Mar	Apr	May	Jun	Jul	Aug	Sep	Oct	Nov	Dec	
h4h project																									
Ethical clearance process (incl. Study protocol)																									
Piloting phase																									
Data collection																									
Intervention phase																									
Feedback to the community																									
Scientific publications																									
Data collection																									
Recruitment																									
Ranas survey																									
Handwashing observations																									
Hand-rinse samples																									
Diary data																									
Contextual factor survey (Pal only)																									
FGDs and interviews																									
Gravit'eau monitoring data																									
Intervention activities																									
Gravit'eau installation (Nig only)																									
Rehabilitation of WASH infrastructure (Pal only)																									
Ranas behaviour change activities																									
Monitoring residual chlorine in water storage (Pal only)																									
Management of WASH infrastructure																									

4.5 Amendments

All of the different modules will be piloted in pilot schools of the study regions and adapted to local needs and circumstances.

Substantial changes to the project set-up; the protocol and relevant project documents will be submitted to all of the Ethics Committees for approval according to the local EC guidelines.

4.6 Withdrawal and discontinuation

Participants may stop their participation at any time and withdraw their consent. However, data obtained prior to participant's withdrawal will be included in analysis to ensure the validity of the study. Data of withdrawn participants are fully anonymised once analysis is completed. Local staff is recruited and employed by Tdh and Cesvi and has to follow the terms and conditions of the local Tdh and Cesvi offices which are written in their work contract.

The overall H4H project or specific project sites can be discontinued due to several reasons by the project leader, such as:

- Ethical concerns (e.g. non-acceptance of proposed technical solutions)
- Insufficient participant recruitment
- Natural hazards (e.g. heavy floods, earthquakes)
- Damage and vandalism of infrastructure, technical failure of interventions
- Alternative interventions and projects at the same facilities not coordinated with us
- Limited access by Tdh or Cesvi staff due to any reason out of their control including pandemics, natural hazards or deterioration of security situation
- Political constraints restricting access to the schools or the project implementation

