4 STUDY DESIGN

The overall project will follow a multi-center cluster-randomized controlled trial (cRCT) design (Figure 2). Prior to this study, a group of schools in the study's target areas were surveyed by the Tdh (in Nigeria) and Cesvi (in Palestine) using the Facility Evaluation Tool for WASH in Schools ([FACET WINS](#)) which is a monitoring tool for WASH delivery services in schools. From these schools a subsample was identified which fulfils certain inclusion criteria (for the inclusion criteria see chapter 5.2 Inclusion criteria).

This subsample was handed over to the local Tdh and Cesvi collaborators who carefully assessed the security situation around the schools. The Tdh and Cesvi collaborators then selected 26 facilities per country, which are most probable to still be accessible for data collection within the next year. These 26 schools will then be allocated to the two arms (intervention vs. control) with covariate constrained stratified randomization using computer-generated randomization code provided by a statistician not involved in any field activities. The intervention arm will receive the full intervention package (handwashing station, behavioural change intervention, capacity development, and management support). The control arm will receive nothing for the duration of the intervention (12 months). Afterwards, they will receive the same intervention package with potential improvements identified in the former intervention group.

In the selected schools, 50 eligible students from each school will be selected from one or two classes within the age group (10-12 years) using random sampling. If the school has at least one class that has ≥ 50 students within the target age group, the sample will be selected from that class, otherwise, the sample can be selected from two classes. For module 1, only 25 students of the 50 students included in the study in each school will be involved. For module 2, the 50 students included in the study in each school will be targeted for assessment using this module. For Module 3, 12 students out of the 25 students targeted with assessment using module 1 will be targeted for assessment using this module.

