4.3 Measures to minimize bias

Different biases might arise in this project. To prevent selection bias and confounding in the two study arms, we will use stratified block randomization to balance the two arms with respect to important baseline characteristics. Due to the nature of the intervention, neither the participants, nor the data collectors of the study, nor the statistician can be blinded. However, to reduce selective counting of CFUs on the hand-rinse samples, the lab workers assessing the number of CFUs will be blinded.

In Module 1, the RANAS and well-being survey, we expect a recall bias and a desirability bias. To minimize the recall bias, participants will not be asked to report any events which have taken place longer than a week ago. To reduce the desirability bias, the people administering the survey will not label themselves clearly as Tdh or Cesvi staff members, because local people know that Tdh and Cesvi often delivers humanitarian aid in the region and might want to impress the Tdh and Cesvi teams. Additionally, to reduce any study personnel bias, the data collectors will all receive a training in advance. Their ID will be recorded in the survey form in order to be able to conduct quality control.

For Modules 1 to 3, data collectors have to upload the completed surveys every night, once they have a stable internet connection. All of the surveys will have the data collector's ID. The PhD student from Swiss TPH will control every second day how long the data collectors took to complete a survey, if certain answers are always the same for specific data collectors and the amount of missing data per survey. In addition, the GPS location of the tablet will be recorded to make sure that the data collection actually took place at the predefined location. These components will be correlated in the statistical software R (version 4.1.3) to test for significant differences between data collectors. In case a data collector delivers significantly different results which are not deemed realistic by the Swiss TPH study team and the local main correspondents of Tdh and Cesvi, the staff will be asked to comply with predefined rules once. If they still do not comply afterwards, they will be replaced. Faulty data from these staff members can then not be used any more for analysing the results of the H4H project. Modules 1-3 will be repeated three months after the intervention and nine months after the intervention.

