To assure the quality and functioning of the Gravit'eau handwashing stations, regular integrity tests and water quality tests will show if the systems are still functional and capable to remove the bacteria. *E.coli* tests of handwashing water will show if there is any recontamination or any integrity problem. In case there is a problem, we will provide an alternative solution (e.g. bucket with soap) and rehabilitate the handwashing systems or dose chlorine into handwashing systems and repeat the test.

In case a school has 25% higher negative health outcomes than the average of all schools, the regional Ministry of Education and Ministry of Health will be consulted to check if this is usual. If not, the study will have to be stopped in this school.

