6.3.1 Datasets to be analysed, analysis populations

For the primary analysis we will use the available case population of primary school students which will be analysed according to the intention-to-treat principles.

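### Section 4.6 lets a school be discontinued because the intervention failed or was refused, without saying that its endline outcome is still observed; the effect could then be overstated

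*Combined protocol and SAP*

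**What the plan says.** Section 4.6 gives a discretionary power with an open list of reasons: "The overall H4H project or specific project sites can be discontinued due to several reasons by the project leader, such as". Three of the listed reasons concern the fate of the intervention itself:

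- "Damage and vandalism of infrastructure, technical failure of interventions"
- "Ethical concerns (e.g. non-acceptance of proposed technical solutions"
- "Political constraints restricting access to the schools or the project implementation"

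Another item covers other projects at the same facility that were not coordinated with the study team.

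On the arms, Section 4 states: "The control arm will receive nothing for the duration of the intervention (12 months". On blinding, Section 4.3 states that "neither the participants, nor the data collectors of the study, nor the statistician can be blinded"; only the laboratory staff counting colonies are blinded.

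On the analysis, Section 6.3.1 says that "we will use the available case population of primary school students which will be analysed according to the intention-to-treat principles". The Synopsis places the primary outcome at endline (Section 6.3 says follow-up, but the sample size in Section 6.2 also refers to one year after baseline). Section 6.4 rules out imputation.

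Two other passages bear on what happens after a failure. For a faulty Gravit'eau station, Section 4.3 says: "In case there is a problem, we will provide an alternative solution (e.g. bucket with soap) and rehabilitate the handwashing systems". Section 5.4.1 lists when an individual participant can be discontinued: withdrawn consent, change of school, absence of at least six months, death, and a school made inaccessible by insecurity.

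**The concern.** A control school has no package that could break down, be refused or prove impossible to install. These reasons for stopping therefore fall on one arm by design. They cannot be applied blind, since each refers to the intervention. They also pick out schools where the package may have worked least.

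Section 4.6 does not distinguish stopping the intervention at a school from stopping outcome measurement there. If measurement stops too, the primary estimate moves from the effect in all randomised schools towards the effect in schools where the package survived. That matters particularly here: Section 2.3.1 says that earlier tests of the station involved no long-term data collection, and Section 3.1.1 asks for evidence on impact and on barriers to implementation. Breakdown and refusal are part of what the trial is meant to measure.

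**Working it through.** **1. The plan's own figure.** Inputs from Section 6.2: 20% against 45%, ICC 0.2, 50 students per school, power 80%, two-sided alpha 0.05 (read from the 95% confidence level).

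- Individual randomisation, pooled variance: n = [1.96·√(2·0.325·0.675) + 0.842·√(0.20·0.80 + 0.45·0.55)]² / 0.25² = 53.9, so 54 per arm.
- Design effect: 1 + (50 − 1)·0.2 = 10.8.
- Schools per arm: 54·10.8/50 = 11.66, so 12, or 13 with the usual extra cluster.
- Simulation (beta-binomial, 40,000 runs, t-test on school proportions): power 78.2% with 12 schools per arm and 81.5% with 13.

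The stated 13 schools per arm is reproduced.

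**2. What follows for a discontinued school.** The primary model uses the endline outcome, on available cases, without imputation. A school with no endline observation contributes nothing. Section 4.6 keeps data collected before a participant withdraws, but data from before endline do not enter the primary model. The intention-to-treat statement fixes the arm in which a school is analysed; it cannot supply a missing outcome. The plan has no sensitivity analysis for lost schools. The Synopsis mentions seven backup schools without a rule for using them, and a replacement would not restore the lost school in any case.

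**3. Size, by assumption.** Let f of 13 intervention schools fail and be absent at endline, let the others reach 45%, let controls be at 20%, and let q be the washing rate in a failed school.

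- All randomised schools: difference = [(13 − f)·0.45 + f·q]/13 − 0.20.
- Available cases: difference = 0.45 − 0.20 = 25.0 points for every f.
- Overstatement = f·(0.45 − q)/13.

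The documents give neither f nor q, so both are varied:

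| f | q = 20% (control rate): true difference | overstatement | q = 32.5% (half the effect): true difference | overstatement | q = 45% |
|---|---|---|---|---|---|
| 1 | 23.1 | 1.9 points (8%) | 24.0 | 1.0 points (4%) | 0 |
| 2 | 21.2 | 3.8 points (18%) | 23.1 | 1.9 points (8%) | 0 |
| 3 | 19.2 | 5.8 points (30%) | 22.1 | 2.9 points (13%) | 0 |

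Percentages are relative to the true difference. The Synopsis counts 26 schools in total, while Section 4 has 26 selected per country. With 26 per arm the divisor becomes 26 and every overstatement in points halves: for q = 20%, 1.0, 1.9 and 2.9 points.

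**4. False-positive rate, worst case.** With no true effect (both arms 20%, ICC 0.2, same simulation), removing the 1, 2 or 3 lowest intervention schools gives spurious mean differences of 1.7, 3.4 and 5.4 points. Two-sided rejection rises from 4.9% to 6.2%, 8.5% and 12.6%. Removing schools at random leaves it at about 5%. This is an upper bound, since discontinuation for failure would not pick exactly the lowest schools. It shows that selective loss, not loss as such, is the problem.

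**The case against.** The strongest reply is that Section 4.6 only permits discontinuation and is silent on endline. Section 6.3.1 states intention to treat. Section 5.4.1 does not list technical failure, vandalism or refusal, so students at a school with a broken station may remain participants. Section 4.3 answers a faulty station with a substitute and repair, and Section 2.3.5 provides for maintenance and timely repairs. When recycled water was refused in Palestine, the component was changed and schools were not dropped (Section 2.3.2). The package also contains behaviour change and management support, so a school with a failed station need not fall back to 20%.

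Much of this stands. It makes the bias a possibility and justifies the range above. It does not close the gap, because no passage says that a discontinued site stays under observation. Where Sections 4.3 and 9.5 speak of stopping at a school or location, it is the study that stops. The repair route covers the handwashing stations, not the rehabilitation works in Palestine or refusal.

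Three stronger readings are tempting, and the documents do not support them:

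- A reader might infer that failed schools do leave the comparison and that the effect is inflated. Endline observation is unspecified, not excluded.
- A reader might infer that Sections 4.3 and 4.6 contradict each other. They can be read in sequence, repair first and discontinuation later; they are unreconciled.
- A reader might infer that removing schools with uncoordinated outside projects also favours the intervention. The documents do not say in which arm such projects would occur, and removing intervention schools that gained from one would bias the other way.

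Nor is every stop one-sided: the Section 4.3 stop for a school with 25% more negative health outcomes than average could remove poorly washing control schools.

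**Conclusion.** The point holds as a gap in the protocol that could bias the primary result. Technical failure, non-acceptance and failed implementation are grounds for discontinuing a site, they arise essentially only in the intervention arm, and nothing keeps such a site in endline measurement. If measurement ends, the available-case estimate could be too favourable.

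With 13 intervention schools and one to three lost, the overstatement ranges from zero to 5.8 points against a planned difference of 25. Where it falls depends on how many schools fail, whether they are absent at endline, and how far washing drops there, none of which the documents state. The figures are risk differences between average school proportions; the planned logistic mixed model would express the effect as an odds ratio, but the loss of schools would work in the same direction.

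**What to change.** In Section 4.6, separate stopping the intervention at a school from stopping outcome measurement there. State that:

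- intervention failure, vandalism, non-acceptance, blocked implementation or an outside project does not by itself end data collection;
- every randomised school that is accessible and still consents is observed at endline and analysed in its allocated arm;
- discontinuations, intervention failures and outside projects are reported by arm and reason.

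Reconcile Section 4.6 with Section 4.3 (the repair route and the health-outcome stop) and with Section 5.4.1. The change leaves the health-outcome stop as it is and does not prescribe when the intervention itself should be stopped.

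The cost is mainly wording, because endline visits to these schools are already planned. The estimate may be smaller if some installations fail. Some schools that reject the package may also withdraw the principal's consent to observation (Section 4, Module 2), so some selective loss may remain and should be reported. The rule is needed before any school is discontinued, since an endline observation that was not made cannot be recovered.

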4.7 End of project

The biological material from the microbiological analysis will be destroyed upon completion of data analysis. Health-related data will be stored in an anonymized form for a minimum of 10 years at a password-protected server of Swiss TPH. Photos, videos and recordings from the project will be stored on a password-protected server of Swiss TPH, tdh, Cesvi or FHNW. If photos or videos contain pictures of people, they will be asked for their oral consent.

5 SELECTION OF STUDY PARTICIPANTS

5.1 Recruitment

Recruitment will differ according to the study modules. Participants will always be recruited within the clusters (primary schools). For the RANAS and well-being survey (Module 1) only 25 students randomly selected out of the 50 students randomly selected from the classes included in the intervention in each school will be targeted. For the handwashing observations (Module 2) and the diary approach (Module 4) the 50 students randomly selected from the classes included in the intervention in each school will be targeted. For the hand-rinse samples (Module 3) only 12 students randomly selected out of the 25 students randomly selected to be targeted with the RANAS and well-being survey will be targeted. For the contextual factor survey (Module 5), all students in the the classes included in the intervention in each school will be invited to participate by delivering a survey to be reported by one of their parents about the contextual factors that could affect hygiene practice of the students.

For the FGDs (Module 6), 10 gender-separated FGDs will take place in the included schools in the intervention arm; 5 FGDs for each gender. However, the saturation factor will be considered when conducting the discussions in the field. Each FGD will be composed of 5-8 selected students and they will be asked for their consent to participate. The selection of the students will be consulted with the school administration, however, selected students need to represent each participating class in the intervention arm of the trial.

Additionally, there will be 5 FGDs composed of 5-8 teachers from included schools in the intervention arm. The teachers invited to participate in the FGDs should be permanent employees in the school and teach one of the classes included in the intervention.

For the KIIs (Module 7), local partners will be consulted on who they see as a suitable stakeholder for an interview. The sampling procedure will therefore be a purposeful sampling. Interviewees will be contacted by the local partners. Interviews will be held until saturation is reached.

5.2 Inclusion criteria

Study participants will be primary school students of schools selected to be included in this study. Schools were selected based on accessibility for the study teams, not having a water source directly connected to the building of the school, having \leq 7000 students. 50 students within the age of 10-12 years old from one or two classes (depending on the number of students in classes) of the 5th-7th grades will be included in the study from each included school. However, due to the large size of the schools and high number of classes in Nigeria, the 50 students will be selected from two classes of the 5th-7th grades close to where the handwashing stations (Gravit'eau) will be positioned. The 50 selected students will be targeted with the handwashing observation (Module 2) and followed for their hygiene-related health outcomes and absenteeism during the course of the study (Module 4), while 25 of them will be targeted with RANAS and well-being survey (Module 1) and 12 of them will be targeted with collecting their hand-rinse samples (Module 3). Students in the selected classes in each school will be delivered a survey to be self-reported by one of their parents about contextual factors that could affect hygiene practice of students (Module 5 in Palestine only).

Inclusion criteria Modules 1-4: students must fulfil all the inclusion criteria:

- Primary school students aged 10-12 years attending included schools
- Students must be in the same school for the course of the study (1 year).

Inclusion criteria Module 5: students must fulfil all the inclusion criteria:

- Students of the classes included in the study in each included school in Palestine

Inclusion criteria Module 6:

- Students of the intervention schools
- Students need to represent each included class in the intervention.

The teachers invited to participate in the FGDs should be

- Aged \geq 18 years old
- Permanent employees in the school
- Teaching one of the classes included in the intervention

Inclusion criteria Module 7:

- The participant needs to be:
 - a) a stakeholder within the community, state, or region of the intervention whose position is related in any way to WASH in schools
 - b) working in one of the intervention schools. They can be hygiene technicians, teachers, school's principal, or in a leading position in the school.
- Aged \geq 18 years old

